12.0 MEASUREMENT OF EFFECT

Endpoints to be evaluated are as follows: Pain reported by the patients during illumination will be measured on a subjective 11-point visual-analog scale (VAS). Treatment response will be evaluated by clinical exam and follow-up photographs at the two follow-up visits.

Endpoints will be:

- 12.1 Pain during illumination (VAS scale 0-10) at 1 min, 5 min, and 10 min
- 12.2 100% lesion clearance rates
- 12.3 75% lesion clearance rates
- 12.4 Visual differences observed in the before-and-after photos
- 12.5 Subject satisfaction questionnaire
- 12.6 Adverse Events- Patients' side effects log (6 days post-PDT) and Investigator assessment.

Regarding lesions clearance rates (items 12.2 and 12.3), the final efficacy outcome will be defined as the lesion counts after two treatments, and these final counts are what the estimated enrolled sample sizes are based on. Lesion status after 1 PDT treatment will also be analyzed, but not considered in the analyses of noninferiority.

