For Question 2, we want to test for non-inferiority between our PDT regimen(s) and, the original 3-hr incubation with occlusion + 10 min red light regimen used for FDA approval [5, 10]. For this purpose, we will do the comparisons using our regimen C, in which patients receive a 1 hour incubation without occlusion + 10 min red light. In the original clinical trial of Ameluz and red light, AK clearance rates were reported to be $78 \pm 15\%$ after 1 PDT treatment (mean \pm SD, n = 31 patients) [15]. To come up with an estimate of what might happen with a shorter red light regimen, we cite the study by Nestor et al 2019 which represents a reasonable surrogate for our proposed short (1-hr) red light regimen [12]. In that study, Ameluz was incubated for 1 hr without occlusion and then illuminated with blue light; the AK clearance rate on the face in 20 patients using Ameluz was 52.3% after 1 PDT treatment, and 97.1% after 2 PDT treatments. Nestor et al

also examined the AK clearance rate in another 20 patients using Levulan, which was 57.7% after 1 PDT treatment, and 94.9% after 2 PDT treatments. The 1-treatment AK clearance rate (57.7%) resembles a previous study that we performed with Levulan and a 1 hr incubation (Kaw et al), yielding an AK clearance on the face of 61% after 1 PDT treatment. This suggests that responses after blue light or red light are very similar. Therefore, we will use the variance for the 1 hr incubation group in the blue light study (Kaw et al) which was $61\% \pm 30\%$ (mean \pm SD; n = 8 patients) [7]. Unfortunately, the Nestor 2019 study did not provide any variance values for their red light data. However, other Ameluz studies in the literature [15] report a typical standard deviation (SD) in the range of 25-30% for the mean AK clearance rate, so we will use 30% as the SD value for our patients in this calculation.

Thus we wish to compare the AK clearance rates for the following two conditions, for statistical non-inferiority:

Group 1 (long 3 hours; control group): $78 \pm 15\%$ (mean \pm SD, n = 31 patients)

Group 2 (short 1 hours; experimental group): $61\% \pm 30\%$ (what power will 10 patients give us?)

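### Section 12.0 rests non-inferiority and the sample size on counts after two treatments, but Section 14.2 sets up that comparison with two one-treatment rates

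*Combined protocol and SAP*

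**What the plan says.** Section 12.0 makes three linked statements about lesion clearance. The outcome is set after the second session: "the final efficacy outcome will be defined as the lesion counts after two treatments". The sample size is said to follow from it: "these final counts are what the estimated enrolled sample sizes are based on". One-treatment data are kept out: "Lesion status after 1 PDT treatment will also be analyzed, but not considered in the analyses of noninferiority".

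Section 14.2 draws its comparison from one-treatment results. For the 3-hour standard it says "In the original clinical trial of Ameluz and red light, AK clearance rates were reported to be" 78 ± 15% after one treatment, in 31 patients. For the 1-hour regimen it relies on an earlier Levulan and blue-light study "yielding an AK clearance on the face of 61% after 1 PDT treatment", with an SD of 30% from 8 patients. These two figures are then listed as Groups 1 and 2, to be compared for non-inferiority.

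Two-treatment rates appear only for blue light. Ameluz clearance "was 52.3% after 1 PDT treatment, and 97.1% after 2 PDT treatments"; for Levulan the text gives clearance "which was 57.7% after 1 PDT treatment, and 94.9% after 2 PDT treatments". Section 14.2 adds that this study "did not provide any variance values for their red light data". Neither two-treatment rate enters Group 1 or Group 2.

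The calculation that closes Section 14.2 gives 10 per group and 80% power for a margin of 25, a true difference of 10, an SD of 13 and two-sided alpha of 0.05. It does not say where the 10 and the 13 come from, or how many treatments they refer to.

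**The concern.** Efficacy is one of two primary endpoints and the one on which the study is powered (Sections 14.1 and 14.2). The comparison displayed for it uses the time point that Section 12.0 excludes, so the two sections cannot both describe the planned test.

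If the final count is tested against the published 78%, the short regimens will have had up to two sessions (Sections 6.1 and 11.3 give the second only if lesions remain) and the standard only one. Any benefit that the standard would have gained from its own second session is credited to the short regimen. A finding of non-inferiority could then partly reflect the extra session rather than the regimen.

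**Working it through.** **1. The plan's own figure.** For 10 versus 10, margin 25, true difference 10 and SD 13, the noncentrality is (25 − 10) / (13 × √(2/10)) = 15 / 5.81 = 2.58 on 18 df. Power is 68.5% at one-sided 0.025 (the stated two-sided 0.05) and 79.9% at one-sided 0.05. The stated 80% is therefore recovered as a one-sided 5% t-test. That is a separate matter; what counts here is which inputs were used.

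**2. Tracing the inputs (Section 14.2).**

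| Source | Treatments | Difference | SD |
|---|---|---|---|
| 3-hour 78% vs 1-hour 61% | one | 78 − 61 = 17 | 15 and 30 |
| Blue light, 97.1% and 94.9% | two | no 3-hour standard to subtract from | none given |
| Calculation sentence | not stated | 10 | 13 |

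The calculation matches neither set of clearance rates. The claim in Section 12.0 that the sample size rests on two-treatment counts has no visible support.

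**3. Effective margin if 78% is the comparator.** Let B2 be the standard's clearance after two treatments. It is not in the documents, so every value below is an assumption. The test passes regimens whose mean exceeds 78 − 25 = 53. Measured against B2, the tolerated deficit is B2 − 53 = 25 + (B2 − 78).

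| Assumed B2 | 78 | 80 | 85 | 90 | 100 |
|---|---|---|---|---|---|
| Effective margin (points) | 25 | 27 | 32 | 37 | 47 |

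The inflation is 0 at B2 = 78 and cannot exceed 100 − 78 = 22 points.

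**4. False-pass rate.** Take a short regimen truly 25 points below B2, which should pass 2.5% of the time. The documents specify no test, so assume a Welch comparison with 10 patients in the short arm and the published group (SD 15, n = 31). Non-inferiority is declared if the lower limit of the two-sided 95% interval exceeds −25. The true mean lies B2 − 78 above the threshold. The standard error is √(15²/31 + 13²/10) = 4.92 with a short-arm SD of 13, and √(15²/31 + 30²/10) = 9.86 with an SD of 30. Simulation with normal data (400,000 runs) gives:

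| Assumed B2 | SD 30 | SD 13 |
|---|---|---|
| 78 | 2.5% | 2.5% |
| 80 | 3.9% | 5.9% |
| 85 | 9.6% | 27.1% |
| 90 | 20.0% | 63.3% |

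**5. A matched one-treatment comparison.** With 61 ± 30% (n = 10) against 78 ± 15% (n = 31), the room to the margin is 25 − 17 = 8 points on a standard error of 9.86. Power is about 11% by the Welch test (12.5% by normal approximation). In the same 10-versus-31 layout, a difference of 10 and an SD of 13 would give about 87%. Most of the shortfall from 80% therefore comes from the mismatch of inputs within Section 14.2, not from the time point.

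**6. A matched two-treatment comparison.** This cannot be computed from the documents. With 10 per arm, margin 25 and one-sided 0.025 (normal approximation), assumed true differences of 0, 5 and 10 give 99%, 93% and 73% power at SD 13, and 46%, 32% and 20% at SD 30.

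**The case against.** The strongest reply is that the unequal number of sessions arises only if the historical 78% is the comparator. Section 1.3 calls regimen C the control. Section 14.2 says the comparisons will be made using regimen C, and its calculation compares each intervention with a control group at 10 per group. With C as control, all arms follow the same session schedule and the bias in steps 3 and 4 disappears. This stands as far as it goes. However, Sections 2.1, 3.1 and 14.1 state the hypothesis against the standard regimen, Sections 3.1 and 14.1 state it for all three regimens including C, and Section 14.2 labels the 3-hour group as control and the 1-hour group as experimental. On the arm C reading, that stated hypothesis is not tested.

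It is also fair to say that the size of the bias rests on an unknown B2, that no test is specified, and that Section 1.2 calls this a pilot study. All three points limit the severity; none removes the contradiction.

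Three stronger readings are tempting and not supported:

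- **That n = 10 was calculated from one-treatment rates.** The 78% and 61% imply a difference of 17 and SDs of 15 and 30, none of which appears in the calculation. What is shown is an unsupported basis, not a wrong time point in the arithmetic.
- **That the bias is as large as the second-session gain in the blue-light data** (97.1 − 52.3 = 44.8 and 94.9 − 57.7 = 37.2 points). Those regimens started at 52–58%. The bias here is B2 − 78, at most 22 points.
- **That an SD of 30% is impossible after two treatments.** On a 0–100% scale the largest SD is √(m(100 − m)), which falls below 30 only when the mean m exceeds 90%. Whether these red-light arms will exceed 90% is unknown.

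**Conclusion.** The contradiction is established from the text alone: Section 12.0 claims a two-treatment basis, and the comparison displayed in Section 14.2 is a one-treatment one. No section supplies a two-treatment rate for the 3-hour standard, and the inputs actually used are unsourced.

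The consequence depends on the comparator. Against the historical 78%, the test favours non-inferiority whenever B2 exceeds 78. The false-pass rates in step 4 rest on assumed B2, normal data, a Welch test and a regimen placed exactly at the margin; they are boundary cases, not a forecast that this trial will reach a wrong conclusion. Against arm C there is no such bias, but the primary hypothesis about the standard is left without a test. Clearance estimates with confidence intervals and the randomised comparisons of A and B with C remain interpretable on either reading. This should be fixed before analysis.

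**What to change.** In Sections 12.0 and 14.2, state whether the comparator is the published standard or arm C, and use the same number of treatments on both sides of any non-inferiority test. Visit 4 counts should not be tested against the one-treatment 78%. There are two ways to match:

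- **Two treatments.** Replace both 78 ± 15% and 61 ± 30% with sourced two-treatment means and SDs, check that each SD is possible for its mean, and recompute the power. This needs a benchmark for the 3-hour regimen that the documents do not contain.
- **One treatment.** Make any comparison with the 78% on the Visit 3 count, once it is confirmed that the benchmark was measured at a comparable time (Visit 3 falls 7–9 weeks after the first session). Report it as an estimate with a confidence interval, and restate its power (about 11% on the displayed inputs). The 80% claim could not be kept for it. Visit 4 can stay the main efficacy time point; moving it is not required.

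In either case, correct the Section 12.0 sentence on the basis of the sample size and give the source and number of treatments for the difference and SD used. If arm C is chosen as control, reword the objective and hypotheses to match.

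The cost is wording and one new calculation. The Visit 3 count is already taken before any second session, so no visit or procedure is added. Two neighbouring issues need their own correction: the SD of 13 against the announced 30, and the 100% and 75% clearance endpoints in Section 12.0 against the mean clearance used in Section 14.2.

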4.2 Exclusion Criteria

- 4.2.1 Pregnant or nursing.
- 4.2.2 Using any topical treatment on their AKs; must stop at least one month prior.
- 4.2.3 Currently undergoing treatment for other cancers with medical or radiation therapy.
- 4.2.4 Patients with a known hypersensitivity to 5-aminolevulinic acid or any component of the study material.
- 4.2.5 Patients with history of a photosensitivity disease, such as porphyria cutanea tarda.

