6.0 TREATMENT PLAN

6.1. Overall descriptive narrative

At the first visit (Visit #1) (Day 1), informed consent will be obtained before starting any study procedures. AK lesions will be counted by [name] and his personally-supervised CCLCM medical student researcher using clinical criteria that include presence of a visible lesion with erythema (pink or red), presence of scale, and a gritty consistency by feel (palpation). Each identified lesion will be marked with a black pen. All the marked lesions will then be counted. As a back-up, the patient's face will be photographed with all the pen-marks in place, for later independent confirmation of lesions counts.

Photographs will be taken two ways. First, documentation of the pen-marked lesions on the face will be taken using CCF i-Phones that are routinely used in our clinic; these digital photographs will be transferred and stored directly in each study patient's electronic (Epic) record.

Second, for photographic documentation of inflammation, the patient will also be photographed by a professional photographer using standardized lighting and multiple views to document the degree of inflammation at baseline.

The skin will be degreased with an alcohol wipe, lesions gently abraded with fine sandpaper, and a thin layer of ALA gel (Ameluz®) will be applied to the entire face. No occlusive dressing will be used. For patients in group **A**, the ALA gel will be left on for 10 min, and then positioned in front of the red light and exposed for 20 min; this is a (10 + 20) regimen. Patients in group **B** and group **C** will receive a (20 + 10) regimen or (60 + 10) regimen, respectively.

Pain will be assessed by asking the patient to rate their perceived pain level on an 11-point VAS scale (0= no pain, 10 = intolerable pain). Patients will be asked to report their VAS score at 1 minute after red light begins, and at the 5 minute mark (when the RhodoLED beeps). They will be asked for a final VAS score immediately after the light is turned off.

To assess side effects, patients will receive a 6-day questionnaire to record their side-effects daily during the coming week, and which asks them to confirm that they completely avoided any sun exposure during the first two days after PDT. Patients will also receive a standard set of instructions for home aftercare that includes Aquaphor emollient, a topical steroid if necessary for comfort, and instructions to wear sunscreen and avoid sunlight for 48 hr.

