6.3 Duration of Follow Up

Patients will be followed until the end of Visit 4, which must occur within a follow-up window of 3-6 months after Visit 1. Thus the maximum duration of F/U is 6 months.

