Privacy and confidentiality: Medical information gathered in this study will be limited to what is recorded in the routine clinical PDT treatment note, along with any study-related notes entered into the electronic medical record (EPIC). Patients must consent to have photographs taken of their facial lesions at each visit, using a standard departmental photographic consent. Consent to allow use of those images in medical publications or presentations that result from the study is voluntary, as the patient will indicate in a checkbox.

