11.0 STUDY PARAMETERS AND DETAILED STUDY CALENDAR

Details of 10% ALA application and red light treatment were described in detail under Section 6.0, “Treatment Plan”. The timing of visits is summarized below and in section 11.5 (“Calendar”).

11.1 **PDT treatment (Visit 1)**

All AK lesions are measured clinically and photographed. The clinician applies 10% ALA gel to entire face, without occlusion, and allows it to incubate if for either 10 min, 20 min, or 60 min, depending upon the study arm assignment. The patient will then be exposed to red light (BF-RhodoLED® device) for either 10 min or 20 min, as per the assigned study arm.

11.2 **Post-treatment assessment of side-effects (Visit 2)**

The patient will return at day 3 (± 1 day) for facial photographs to document their erythema reaction. They will also be asked about their side-effects, and insure that they know to fill out the side-effects questionnaire during the 6 days post-PDT.

11.3 **PDT treatment (Visit 3)**

This will occur 8 weeks (± 1 week) after Visit 1. All AK lesions will be measured clinically and photographed and if any remain, then the same PDT treatment regimen used at Visit 1 will be employed again here for a second round of treatment.

11.4 **Final observation (Visit 4)**

This will occur 3-6 months after Visit 1. The subject will return for final skin exam, lesion counts, and photography. A patient satisfaction questionnaire will also be administered at this visit. The large scheduling visit window is designed to maximize the likelihood of patient compliance, since many patients with AK are retirees who spend many months traveling and spend their winters in warmer climates far from Cleveland.

11.5 **Study Calendar**

CALENDAR. Timeline of procedures for patients enrolled in the study.

	VISIT 1 PDT treatment session #1	VISIT 2 Photos of skin redness	VISIT 3 PDT treatment session #2	VISIT 4 Final lesion counts
Scheduled visit: → Procedure: ↓	Day 1	Day 3 ± 1 day	Week 8 ± 1 week	Month 3-6
Sign informed consent	X			
Examine patient, mark each lesion with a pen, and count the lesions	X		X	X
Take photographs in our professional studio (frontal view and side views) to document inflammation.	X	X		
Take photographs using clinic iPhone camera to document lesion counts (pen-marks)	X		X	X

Apply topical ALA gel and incubate for 10, 20, or 60 min prior to turning on the light source (as per assigned study arms A, B, or C, respectively)	X		X	

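### No passage requires other treatment of facial AKs between Visit 1 and Visit 4 to be asked about, recorded or handled, so a lesion removed by other means counts as cleared by the study regimen

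*Combined protocol and SAP*

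**What the plan says.** Section 12.0 sets the efficacy endpoints as 100% and 75% lesion clearance rates and states that "the final efficacy outcome will be defined as the lesion counts after two treatments". It attaches no condition about lesions treated by other means. Section 6.3 fixes the timing: "Patients will be followed until the end of Visit 4, which must occur within a follow-up window of 3-6 months after Visit 1".

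The only rule on other AK treatment is exclusion 4.2.2: "Using any topical treatment on their AKs; must stop at least one month prior". It concerns topical products before entry. The one other exclusion about concurrent treatment, 4.2.3, is "Currently undergoing treatment for other cancers with medical or radiation therapy", which does not concern AKs.

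After enrolment:
- Section 11.4 describes Visit 4 as follows: "The subject will return for final skin exam, lesion counts, and photography". A satisfaction questionnaire is added. There is no question about treatment since the last visit.
- Sections 6.1 and 11.3 (Visit 3) and both calendars (Study Schema and Section 11.5) contain no such item.
- The diary is short and is about side effects (Section 6.1): "patients will receive a 6-day questionnaire to record their side-effects daily during the coming week".
- Under Privacy and confidentiality in Section 10.0: "Medical information gathered in this study will be limited to what is recorded in the routine clinical PDT treatment note", together with study-related notes in the electronic record.
- Section 14 has no rule for lesions treated outside the protocol.

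Section 1.1 names cryotherapy, excision and several topical drugs as available AK treatments.

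**The concern.** Efficacy is read from a whole-face count taken up to six months after the first PDT. Participants have at least 10 facial AKs (Section 4.1), and Section 11.4 explains the wide Visit 4 window by saying that "many patients with AK are retirees who spend many months traveling and spend their winters in warmer climates". If a residual lesion is frozen, excised or treated topically in that time, it is missing from the Visit 4 count and scores as a success of the assigned regimen.

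The error has a direction. Only residual lesions can be removed in this way, so a regimen that leaves more of them has more to gain. In a non-inferiority comparison that favours the conclusion the trial hopes to reach. It is strongest against the published 3-hour rate named in Sections 14.1 and 14.2, because that rate is fixed and cannot shift with it. Treatment elsewhere before Visit 3 could also affect whether the second PDT is given, since Sections 6.1 and 11.3 make it depend on lesions remaining.

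**Working it through.** **The plan's own calculation.** Section 14.2 gives margin 25, true difference 10, SD 13, n = 10 per group, 80% power, two-sided alpha 0.05. With n = 2 × SD² × (z₁₋α + z₀.₈)² / (25 − 10)²:
- one-sided 0.025: 2 × 169 × (1.960 + 0.842)² / 225 = 11.8, so 12 per group;
- one-sided 0.05: 2 × 169 × (1.645 + 0.842)² / 225 = 9.3, so 10 per group.

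The stated n matches a one-sided 0.05 test. That gap is a separate matter, and nothing below changes the sample size.

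**Shift in mean clearance.** Let m be true mean clearance and f the fraction of patients whose residual lesions are all treated elsewhere, unrelated to m. Then observed mean = m + f(100 − m), and the shift is f(100 − m). The documents give no value for f; 10% and 20% are assumptions. The values of m come from Section 14.2: 97.1% and 94.9% are two-treatment rates after 1-hour incubation with blue light, and 61% is the one-treatment figure that the protocol uses for its experimental group.

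| m | f = 10% | f = 20% |
|---|---|---|
| 97.1% | 0.1 × 2.9 = +0.3 | 0.2 × 2.9 = +0.6 |
| 94.9% | 0.1 × 5.1 = +0.5 | 0.2 × 5.1 = +1.0 |
| 61% | 0.1 × 39 = +3.9 | 0.2 × 39 = +7.8 |

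The largest shift is 7.8 / 25 = 31% of the margin.

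**Effect on a deficit.** Take 78% for the published control and 53% for a regimen exactly at the margin (78 − 25).
- Against the fixed published rate at f = 20%: 53 + 0.2 × 47 = 62.4, so the deficit reads 78 − 62.4 = 15.6 points.
- Between two trial arms affected at the same rate, differences shrink by (1 − f): 25 × 0.8 = 20 points.

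**False non-inferiority at that deficit.** Setup: control mean 78, regimen mean 53, SD 13 in each, 10 v 10, pooled t test at one-sided 0.025, simulated 400,000 times. Each patient in the regimen arm is set to 100% with probability f. This also widens the spread: SD = √[(1 − f) × 169 + f(1 − f) × 47²], which is 18.7 at f = 10% and 22.1 at f = 20%.

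| f | Observed mean | False non-inferiority |
|---|---|---|
| 0 | 53.0 | 2.5% |
| 10% | 57.7 | about 6.5% |
| 20% | 62.4 | about 16% |

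**Threshold endpoints.** A patient with 10 lesions, 6 cleared by PDT and 4 removed elsewhere, scores 100% instead of 60% and passes both 12.2 and 12.3. With 10 patients per arm, that one patient moves each rate by 10 percentage points.

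**The case against.** The strongest reply is that the effect may be trivial. The endpoint is the count after two treatments, and the only two-treatment rates in the protocol are 94.9% and 97.1%. At those levels few lesions are left to be treated elsewhere, and even f = 20% adds no more than about a point. This stands as the low end of the range. It does not settle the matter, because those rates are from blue light and the protocol itself plans on 61%.

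Second, no passage says that patients are treated elsewhere. Section 11.4 mentions travel only to justify the visit window. Lesions remaining at Week 8 receive a second study PDT, and Visit 4 may follow as little as 4 weeks later (taking 3 months as 13 weeks, 13 − 9). This also stands: the frequency is unknown.

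Third, a reader might infer that the information will not exist and that no later correction is possible. The documents do not support that. The Section 10.0 text is a privacy paragraph and allows study-related notes, and the electronic case report forms mentioned in Section 13.1 are not reproduced. What can be said is that no passage ensures collection.

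Fourth, a reader might infer that a general bar on other AK treatment already exists and need only be extended. It does not: 4.2.2 is confined to topical products, so cryotherapy and excision are not restricted even at entry.

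Finally, a reader might shift the mean while leaving the SD at 13, which gives false non-inferiority of 11.6% at f = 10% and 33.4% at f = 20%. When whole patients move to 100%, the SD rises too, and the figures are roughly half those.

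The study is described as a pilot (Section 1.2), which lowers the stakes. Its second primary objective is nevertheless a non-inferiority claim.

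**Conclusion.** The gap is real. Followed as written, the plan credits to the study regimen any facial AK removed by other means before Visit 4, and it does not ensure that the analyst will know. The bias runs towards non-inferiority and has nothing to offset it when the comparator is the published 3-hour rate.

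Its size depends on two unknowns: how often it happens and how well the regimens work. With 10-20% of patients affected, the inflation runs from about 0.3 points (true clearance 97.1%) to 7.8 points (true clearance 61%). In the least favourable case examined, a true 25-point deficit, the false non-inferiority rate goes from 2.5% to about 6.5-16%. That last result assumes normally distributed clearance with SD 13, contamination of the regimen arm only, and complete treatment of the residual lesions in the affected patients.

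The documents do not show that outside treatment is common or that the result would be invalid. They do show an avoidable bias in a primary endpoint, with a cheap remedy that works best if in place before follow-up. It should be corrected.

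**What to change.** 1. **Section 11 and both calendars:** at Visits 3 and 4, ask about and record any non-protocol treatment of facial AKs since the previous count (type, date, site on the face).
2. **Section 12.0:** count each lesion so treated before Visit 4 as not cleared, by adding it to the residual count. Because the protocol takes whole-face counts, identify these lesions from the recorded site and the existing pen-mark photographs. Where a lesion cannot be matched, score the patient as not meeting 12.2 or 12.3.
3. **Section 14:** report the unadjusted Visit 4 count as a sensitivity analysis.

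No restriction on other care is proposed. Whether to have one is for the investigator, and the recording and scoring rules work either way.

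Cost: a short amendment, one question at two existing visits, some matching of photographs in affected patients, and slightly less favourable measured clearance. The sample size does not change.
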